Appendix 4. Tanner Stages*

1. Pubic hair (male and female)	
Tanner I	no pubic hair at all (prepubertal Dominic state)
Tanner II	small amount of long, downy hair with slight pigmentation at the base of the penis and scrotum (males) or on the labia majora (females)
Tanner III	hair becomes more coarse and curly, and begins to extend laterally
Tanner IV	adult-like hair quality, extending across pubis but sparing medial thighs
Tanner V	hair extends to medial surface of the thighs
2. Genitals (male) (One standard deviation around mean age)	
Tanner I	Testes, scrotum, and penis about same size and proportion as in early childhood
Tanner II	Enlargement of scrotum and testes; skin of scrotum reddens and changes in texture; little or no enlargement of penis (10.5-12.5)
Tanner III	Enlargement of penis, first mainly in length; further growth of testes and scrotum (11.5-14)
Tanner IV	Increased size of penis with growth in breadth and development of glans; further enlargement of testes and scrotum and increased darkening of scrotal skin (13.5-15)
Tanner V	Genitalia adult in size and shape
3. Breasts (female)	
Tanner I	no glandular tissue: areola follows the skin contours of the chest
Tanner II	breast bud forms, with small area of surrounding glandular tissue; areola begins to widen
Tanner III	breast begins to become more elevated, and extends beyond the borders of the areola, which continues to widen but remains in contour with surrounding breast
Tanner IV	increased breast size and elevation; areola and papilla form a secondary mound projecting from the contour of the surrounding breast
Tanner V	breast reaches final adult size; areola returns to contour of the surrounding breast, with a projecting central papilla.

* Chart referenced from Marshall WA, Tanner JM, variations in the pattern of pubertal changes in boys and girls {[Marshall 1969](#), [Marshall 1970](#)}

Appendix 5. Pregnancy Precautions, Definition for Female of Childbearing Potential, and Contraceptive Requirements

1) Definitions

a) Definition of Childbearing Potential

For the purposes of this study, a female born subject is considered of childbearing potential following menarche until becoming post-menopausal, unless permanently sterile or with medically documented ovarian failure.

Women of any age with amenorrhea of > 12 months may be considered post-menopausal if their follicle stimulating hormone (FS) level is in the post-menopausal range and they are not using hormonal contraception or hormonal replacement therapy. Permanent sterilization includes hysterectomy, bilateral oophorectomy, or bilateral salpingectomy in a female subject of any age.

b) Definition of Male Fertility

For the purposes of this study, a male born subject is considered fertile after the initiation of puberty unless permanently sterile by bilateral orchidectomy or medical documentation.

2) Study Drug Effects on Pregnancy and Hormonal Contraception

Data from clinical pharmacokinetic interaction studies of SOF have demonstrated that there is no reduction in the clinical efficacy of hormonal contraception. Non-clinical toxicity studies of SOF have demonstrated no adverse effect on fertility or embryo-fetal development

Data from clinical pharmacokinetic interaction studies of VEL have demonstrated that there is no reduction in the clinical efficacy of hormonal contraception. Non-clinical toxicity studies of GS-5816 have demonstrated no adverse effect on fertility or embryo-fetal development.

However, the risks of treatment with SOF/VEL FDC during pregnancy in humans have not been evaluated. Please refer to the latest version of the investigator's brochure for additional information.

3) Contraception Requirements for Female Subjects of Childbearing Potential

The inclusion of female subjects of childbearing potential requires using at least an acceptable effective contraceptive measure. They must have a negative serum pregnancy test at Screening and a negative pregnancy test on the Day 1 visit prior to enrollment. A pregnancy test will be performed at the Posttreatment Week 4 visit. They must also agree to one of the following from Screening until 30 days of the last dose of SOF/VEL FDC.

- Complete abstinence from intercourse of reproductive potential. Abstinence is an acceptable method of contraception only when it is in line with the subject's preferred and usual lifestyle.

Or

- Consistent and correct use of 1 of the following methods of birth control listed below.
 - Intrauterine device (IUD)
 - Intrauterine hormone-releasing system (IUS)
 - Tubal sterilization
 - Essure micro-insert system
 - Vasectomy in the male partner
 - Barrier methods (one female barrier and one male barrier must be used in combination)
 - Female barriers: Diaphragm with spermicide or Cervical cap with spermicide
 - Male barriers: Male condom (with or without spermicide)
 - Hormonal methods
 - Oral contraceptives (either combined or progesterone only)
 - Injectable progesterone
 - Implants of levonorgestrel or etonorgestrel
 - Transdermal contraceptive patch
 - Contraceptive vaginal ring

Female subjects must also refrain from egg donation and in vitro fertilization during treatment and until at least 30 days after the last dose of SOF/VEL FDC.

4) Contraception Requirements for Male Subjects

During the study, male subjects with female partners of childbearing potential should use condoms until 30 days after the last dose of SOF/VEL FDC treatment when engaging in intercourse of reproductive potential. If their female partner is of childbearing potential (as defined above), their female partner must use 1 of the methods of birth control listed above from the date of Screening until 30 days after the last dose of SOF/VEL FDC.

Male subjects must agree to refrain from sperm donation until 30 days after the last dose of SOF/VEL FDC.

5) Unacceptable Methods of Contraception

Birth control methods that are unacceptable include periodic abstinence (e.g., calendar, ovulation, symptothermal and post-ovulation methods), withdrawal (coitus interruptus), spermicides only, and lactational amenorrhea method (LAM). Female condom and male condom should not be used together.

6) Procedures to be Followed in the Event of Pregnancy

Subjects will be instructed to notify the investigator if they become pregnant at any time during the study, or if they become pregnant within 30 days of the last dose of SOF/VEL FDC. Subjects who become pregnant or who suspect that they are pregnant must report the information to the investigator and discontinue study drug immediately. Subjects whose partner has become pregnant or suspects she is pregnant must report the information to the investigator.

Instructions for reporting pregnancy, partner pregnancy, and pregnancy outcome are outlined in Section [7.6.2.1](#).

## LIST OF ABBREVIATIONS

AE	adverse event
ALT	alanine aminotransferase
ANOVA	analysis of variance
AST	aspartate aminotransferase
BLQ	below the limit of quantitation
BMI	body mass index
CDC	Centers for Disease Control
CFR	Code of Federal Regulations
CI	confidence interval
CK	creatinine kinase
CSR	clinical study report
DMC	data monitoring committee
ECG	electrocardiogram
eCRF	electronic case report form
eGFR	estimated glomerular filtration rate
EOT	end of treatment
FAS	Full Analysis Set
FDC	Fixed Dose Combination
FU	follow-up
Gilead	Gilead Sciences, Inc.
GT	genotype
Hb	hemoglobin
HCV	hepatitis C virus
HLT	high level term
HLGT	high level group term
ICH	International Conference on Harmonization (of Technical Requirements for Registration of Pharmaceuticals for Human Use)
ID	identification
IFN	interferon
LLT	lower level term
LLOQ	lower limit of quantitation
MedDRA	Medical Dictionary for Regulatory Activities
PedsQL™	Pediatric Quality of Life Inventory™
PK	pharmacokinetics
PT	preferred term
Q1	first quartile
Q3	third quartile
RBV	ribavirin
RNA	ribonucleic acid

SAE	serious adverse event
SAP	statistical analysis plan
SI (units)	International system of units
SOC	system organ class
SOF	sofosbuvir
SVR	sustained virologic response
SVRx	sustained virologic response x weeks after stopping study drug
TEAE	treatment-emergent adverse events
TFLs	tables, figures, and listings
TND	target not detected
ULN	upper limit of normal
VEL	velpatasvir
VF	virologic failure
WBC	white blood cell
WHO	World Health Organization

## PHARMACOKINETIC ABBREVIATIONS AND DEFINITIONS

AUC	area under the plasma/serum concentration versus time curve
AUC tau	area under the plasma/serum concentration versus time curve over the dosing interval
C last	last observed quantifiable serum/plasma/PBMC concentration of the drug
CL/F	apparent oral clearance after administration of the drug: CL/F = Dose/AUC inf , where "Dose" is the dose of the drug
C max	maximum observed plasma/serum concentration of drug
C tau	observed drug concentration at the end of the dosing interval
t 1/2	estimate of the terminal elimination half-life of the drug in serum/plasma, calculated by dividing the natural log of 2 by the terminal elimination rate constant ( $\lambda_z$ )
T last	time (observed time point) of C last
T max	time (observed time point) of C max

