- To evaluate the emergence of viral resistance to SOF and VEL during treatment and after cessation of treatment
- To evaluate the effect of treatment with SOF/VEL FDC on quality of life as measured by PedsQL™ Pediatric Quality of Life survey
- To evaluate the effect of SOF/VEL FDC on growth and development of pediatric subjects during and after treatment
- To evaluate the acceptability, including palatability, of formulations used in the study

The exploratory objective of this study is:

Study Design:

Open-label, multi-cohort, two-part study evaluating the PK, safety, and antiviral activity of SOF/VEL FDC in pediatric subjects with chronic HCV infection.

Pediatric subjects with chronic HCV infection of any HCV genotype, including indeterminate or mixed genotypes, will be enrolled. Both treatment-naïve and treatment-experienced subjects will be eligible, with at least 20 and up to 40 subjects overall allowed to be treatment-experienced.

PK Lead-in Phase: The PK Lead-in Phase will evaluate and/or confirm age appropriate SOF/VEL FDC doses by analyzing PK, safety, and antiviral activity of SOF/VEL FDC through 7 days of dosing with intensive PK sample collection at steady state on Day 7. Three sequential age-based cohorts of at least 17 subjects each will be enrolled:

- Cohort 1: 12 to < 18 years old
- Cohort 2: 6 to < 12 years old
- Cohort 3: 3 to < 6 years old
 - At least 6 subjects weighing \geq 17 kg
 - At least 6 subjects weighing < 17 kg

PK Lead-in subjects in each cohort will immediately roll over into the Treatment Phase as they complete Day 7 of the PK Lead-in Phase. They will continue dosing with the same dose of SOF/VEL FDC with no interruption of study drug administration and will follow the Treatment Phase visit schedule for all subsequent visits.

The PK and safety data through Day 7 of each cohort will be reviewed to confirm the appropriateness of the SOF/VEL FDC dose for the Treatment Phase in that age group as well as to determine the dose to be evaluated in the PK Lead-in Phase of the next age cohort.

Treatment Phase: The Treatment Phase will be initiated sequentially by age group after confirmation of the age-appropriate SOF/VEL FDC dose as follows (including subjects that participated within the PK Lead-in Phase):

- Group 1: Approximately 100 subjects aged 12 to < 18 years
— Includes subjects enrolled in Cohort 1
- Group 2: Approximately 100 subjects aged 3 to < 12 years
— Includes subjects enrolled in Cohorts 2 and 3

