On-Treatment assessments will include: complete or symptom-directed physical examination (as applicable), vital signs, body height and weight, AEs and serious adverse events (SAEs), concomitant medications, pregnancy prevention counseling (all subjects \geq 12 years of age and subjects $<$ 12 years of age at the discretion of the investigator based on subject's pubertal status), medication compliance, subject dosing diary, safety laboratory tests (including hematology, chemistry, and coagulation), TSH (at Screening, Week 12 and Early Termination), HCV RNA, HBV DNA for HBcAb positive subjects at Screening, HCV viral sequencing sampling, urine pregnancy testing (females of childbearing potential only), urinalysis, IL28B (at Day 1 only), a quality of life survey (at Day 1, Week 12 and Early Termination), Tanner Pubertal Stage assessment (at Day 1, Week 12 and Early Termination), and radiographic bone age assessment (at Day 1 and Early Termination). Acceptability will be completed by the subject (including palatability assessment) and parent/legal guardian (at Day 1, Week 12 and Early Termination).

CCI

On-treatment PK assessments include the following:

- For subjects enrolled in the PK Lead-in Phase (Cohorts 1, 2 and 3)
 - Completion of a Subject Dosing Diary from Day 1 through 7
 - Intensive PK sampling on Day 7

Cohorts 1 and 2:

For Cohorts 1 and 2, plasma samples will be collected for PK analyses following dosing of study drug on Day 7 at the following time points: 0 (predose), 0.5, 1, 2, 3, 4, 6, 8, and 12 hours postdose (with predose also serving as t=24).

Cohort 3:

For Cohort 3, plasma samples for PK analyses will be collected at the following time points: 0 (predose), 0.5, 1, 2, 3, 4, 8, and 12 hours postdose (with predose also serving as $t=24$).

For all Cohorts, following completion of the Day 7 visit, subjects will then return for scheduled study visits outlined in the Treatment Phase and will continue dosing with SOF/VEL FDC with no interruption of study drug administration.

- For all enrolled subjects:
 - Single sparse PK sample collected anytime at Week 1 and Week 12
 - Two sparse PK samples collected at Week 4 and Week 8,
CCI [REDACTED]
 - Predose
 - Between 15 minutes to 4 hours postdose

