With approximately 100 subjects enrolled into 12 to < 18 years of age group and approximately 100 subjects enrolled into 3 to < 12 years of age group, a 2-sided 95% exact confidence interval of the SVR12 rate in each age group will extend at most 20%

This study will be conducted in accordance with the guidelines of Good Clinical Practice (GCP) including archiving of essential documents.

GLOSSARY OF ABBREVIATIONS AND DEFINITION OF TERMS

° C	degrees Celsius
° F	degrees Fahrenheit
β-hCG	beta-human chorionic gonadotropin
AAT	alpha-1 anti-trypsin
AE	adverse event
ALT	alanine aminotransferase (also SGPT)
ANC	absolute neutrophil count
ANOVA	analysis of variance
APRI	AST to platelet ratio index
APTT	activated partial thromboplastin time
AST	aspartate aminotransferase (also SGOT)
AUC _{tau}	area under the plasma concentration versus time curve over the dosing interval (tau)
BCRP	breast cancer resistance protein
BLQ	below the lower limit of quantification
BMI	body mass index
CatA	cathepsin A
CES1	carboxylesterase
CHF	congestive heart failure
CK	creatinine kinase
C _{last}	last observed quantifiable drug concentration
CL/F	apparent oral clearance after administration of the drug
C _{max}	the maximum observed serum/plasma/peripheral blood mononuclear (PBMC) concentration of drug
C _{tau}	observed drug concentration at the end of the dosing interval (tau)
CRF	case report form(s)
CRO	contract (or clinical) research organization
CSR	clinical study report
CVA	cerebral vascular accident
DAA	direct acting antiviral
dL	deciliter
DNA	deoxyribonucleic acid
DMC	data monitoring committee
ECG	electrocardiogram
eCRF	electronic case report form(s)
eSAE	electronic Serious Adverse Event
ESPGHAN	European Society for Paediatric Gastroenterology
EU	European Union
FAS	full analysis set

FDA	(United States) Food and Drug Administration
FDC	Fixed-Dose Combination
FEV ₁	forced expiratory volume in one second
FSH	follicle stimulating hormone
GCP	Good Clinical Practice (Guidelines)
GCSF	granulocyte colony stimulating factor
GFR	glomerular filtration rate
GGT	gamma glutamyl transferase
GLSM	geometric least-squares mean
GMR	geometric mean ratio
GSI	Gilead Sciences, Inc.
GT	genotype (viral)
HAV	hepatitis A Virus
Hb	hemoglobin
HbA _{1c}	hemoglobin A _{1c}
HBsAg	hepatitis B surface antigen
HBsAb	hepatitis B surface antibody
HBcAb	hepatitis B core antibody
HBV	hepatitis B virus
HCC	hepatocellular carcinoma
HCV	hepatitis C virus
HDPE	high-density polyethylene
HIV	human Immunodeficiency Virus

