5.2. Dosage and Administration of SOF/VEL FDC

Subjects 12 to < 18 years old enrolled in the PK Lead-in Cohort 1 or in the Treatment Phase

SOF/VEL FDC 400/100 mg tablets will be administered once daily with or without food. Subjects determined unable to swallow the placebo to match the 400/100 mg SOF/VEL FDC tablet will be re-assigned to 2 x 200/50 mg SOF/VEL FDC tablets daily. Subjects unable to swallow the reduced strength SOF/VEL FDC 200/50 mg tablets will be reassigned to SOF/VEL FDC oral granule formulation (8 x 50/12.5 mg packets).

Subjects 6 to < 12 years old enrolled in the PK Lead-in Cohort 2 or in the Treatment Phase

SOF/VEL FDC 200/50 mg tablets will be administered once daily with or without food. Subjects determined unable to swallow the placebo tablet 200/50 mg SOF/VEL FDC will be reassigned to SOF/VEL FDC oral granule formulation (4 x 50/12.5 mg packets).

Subjects 3 to < 6 years old enrolled in the PK Lead-in Cohort 3 or in the Treatment Phase

SOF/VEL FDC 50/12.5 mg oral granules in a packet will be administered once daily with or without food. Subjects who weigh ≥ 17 kgs will be assigned to 200/50 mg SOF/VEL FDC oral granules (4 x 50/12.5 mg packets) and subjects who weigh < 17 kgs will be assigned to 150/37.5 mg SOF/VEL FDC oral granules (3 x 50/12.5 mg packets). The instructions dosing of oral granules are defined in Section 5.2.1.

Subjects should be instructed that if vomiting occurs within 3 hours of dosing an additional tablet or granules packets should be taken according to the dosing instructions above. If vomiting occurs more than 3 hours after dosing, no replacement dose is required that day.

If a dose is missed and it is within 18 hours of the normal regular scheduled time, subjects should be instructed to take the tablet or granules as soon as possible and then follow with the next dose at the usual scheduled time.

If it is after 18 hours then it is considered a missed dose. Subjects should be instructed to take the next dose at the usual next scheduled time. Subjects should be instructed not to take a double dose.

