8.1.2. Primary Endpoint

The appropriateness of the SOF/VEL FDC dose will be assessed by evaluating the steady-state PK of the VEL, SOF, and GS-331007 at Day 7. Estimated PK parameters will include C_{max} , T_{max} , C_{last} , T_{last} , C_{tau} , AUC_{tau} , CL/F , Vz/F and $t_{1/2}$, as appropriate). The primary PK endpoint of the PK Lead-in Phase is AUC_{tau} of VEL, SOF, and its major metabolite (GS-331007).

The primary endpoint of the Treatment Phase is assessment of any AEs with a focus on AEs that lead to discontinuation of study drug.

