## **8. PHARMACOKINETIC ANALYSES**

### **8.1. PK Analysis in the PK Lead-in Phase (Intensive PK Analysis)**

Intensive PK Analysis will be performed using the Lead-in Phase PK Analysis Set. Concentrations of SOF, GS-331007, GS-566500 and VEL from subjects in the PK lead-in Phase over sampling time will be listed and summarized for each age cohort using descriptive statistics (n, arithmetic mean, geometric mean and its 95% confidence interval, coefficient of variation [%CV], SD, median, Q1, Q3, minimum, and maximum) by nominal time. For Cohort 1 and 2, plasma samples will be collected for PK analyses following dosing of study drugs on Day 7 at the following time points: 0 (predose), 0.5, 1, 2, 3, 4, 6, 8, and 12 hours postdose. For Cohort 3, plasma samples for PK analyses will be collected at the following time points: 0 (predose), 0.5, 1, 2, 3, 4, 8, and 12 hours postdose. PK parameters from subjects in the PK lead-in Phase for each age cohort will be summarized (e.g;  $AUC_{\tau}$ ,  $AUC_{last}$ ,  $C_{max}$ ,  $T_{max}$ ,  $C_{last}$ ,  $T_{last}$ ,  $C_{\tau}$ ,  $T_{1/2}$ , volume of distribution and clearance [CL/F], as appropriate).

SOF, GS-331007 and VEL exposures ( $AUC_{\tau}$ ,  $C_{max}$ , and  $C_{\tau}$ , if applicable) in each age cohort will be compared with SOF/VEL adult populations. The primary endpoint of this analysis will be evaluated by carrying out an analysis of variance (ANOVA) for log-transformed SOF, GS-331007 and VEL  $AUC_{\tau}$ . The secondary endpoints of this analysis will be the  $C_{max}$  of SOF, VEL and GS-331007 and  $C_{\tau}$  of VEL. The 90% confidence intervals will be constructed for the ratio of geometric means of each PK parameters.

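### The SAP's only formula for CL/F is the single-dose form (Dose/AUCinf), but CL/F and volume are to be summarized from a steady-state Day 7 profile; minor, and confined to descriptive summaries

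*SAP*

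**What the plan says.** The SAP's section of pharmacokinetic abbreviations and definitions has the entry "apparent oral clearance after administration of the drug: CL/F = Dose/AUC", where AUC carries the subscript inf. The same list defines AUCtau as "area under the plasma/serum concentration versus time curve over the dosing interval", but the CL/F entry does not use it. No other formula for CL/F appears in the SAP or the protocol; the protocol glossary gives only "apparent oral clearance after administration of the drug".

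The profile in question is a multiple-dose one. The protocol synopsis plans "intensive PK sample collection at steady state on Day 7", and protocol section 8.1.2 states: "The appropriateness of the SOF/VEL FDC dose will be assessed by evaluating the steady-state PK of the VEL, SOF, and GS-331007 at Day 7". Dosing is once daily; protocol section 5.2 says of adolescents, for example, "SOF/VEL FDC 400/100 mg tablets will be administered once daily with or without food". Sampling runs to 12 hours, and the predose sample is reused to close the interval: "8, and 12 hours postdose (with predose also serving as t=24").

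SAP section 8.1 summarizes parameters from these profiles by age cohort. Its list, given as examples, names AUCtau and AUClast, and ends with "volume of distribution and clearance [CL/F], as appropriate". AUCinf is not in it. The protocol synopsis and section 8.1.2 also name CL/F and Vz/F among the estimated parameters.

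**The concern.** Dose divided by AUC to infinity gives apparent clearance after a single dose. At steady state with linear kinetics, the area over one dosing interval equals that single-dose area, so the matching formula is Dose/AUCtau. Extrapolating a steady-state curve to infinity adds the tail of every earlier dose to the denominator, while the numerator stays at one dose. The result is too low whenever the drug accumulates.

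The formula also calls for a quantity that the analysis section does not list. Whoever programs the parameters must either derive AUCinf from the Day 7 curve, which is biased, or depart from the written definition without a record of it. At stake are the reported pediatric CL/F and volume summaries. Because the error depends on half-life, it need not be the same for sofosbuvir, GS-331007 and velpatasvir.

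**Working it through.** The plan gives no CL/F value to reproduce, so the check is of the formula against the design.

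**Inputs**
- Formula for CL/F: Dose/AUCinf (SAP pharmacokinetic definitions).
- Dosing interval tau: 24 h, from once-daily dosing (protocol section 5.2).
- State: steady state, Day 7 (protocol synopsis and section 8.1.2).
- Terminal half-life: not in the documents. Values from 2 to 24 h are assumed below.
- Absorption rate ka: not in the documents. Values of 0.5, 1 and 2 per h are assumed.

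**Formulas** (one compartment, linear kinetics, lambda_z = ln2/t1/2)
1. At steady state, AUCtau = Dose/(CL/F).
2. AUCinf extrapolated from the same profile = AUCtau + Ctau/lambda_z.
3. SAP CL/F divided by true CL/F = AUCtau/AUCinf.
4. With very fast absorption this is 1 - exp(-ln2 x 24/t1/2), so the understatement is exp(-ln2 x 24/t1/2).
5. With first-order absorption, (Ctau/lambda_z)/AUCtau is approximately [ka/(ka - lambda_z)] x exp(-lambda_z x tau)/[1 - exp(-lambda_z x tau)].

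**Worked case**, half-life 12 h and ka = 1 per h: lambda_z = 0.693/12 = 0.0578, and exp(-lambda_z x 24) = 0.25. Then (1/0.9422) x 0.25/0.75 = 0.354, and the ratio is 1/1.354 = 0.739. CL/F comes out 26% too low.

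**Results.** The last two columns come from adding up repeated doses numerically, over ka 0.5 to 2 per h.

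| Assumed half-life | exp(-ln2 x 24/t1/2) | SAP CL/F ÷ true CL/F | Understatement |
|---|---|---|---|
| 2 h | 0.0002 | 0.999-1.000 | 0.1% or less |
| 6 h | 0.0625 | 0.920-0.934 | 7-8% |
| 12 h | 0.250 | 0.726-0.744 | 26-27% |
| 18 h | 0.397 | 0.584-0.598 | 40-42% |
| 24 h | 0.500 | 0.485-0.496 | 50-52% |

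The simple exponential is a close approximation; absorption adds up to about 2 percentage points. If Vz/F is obtained as (CL/F)/lambda_z, it falls by the same fraction. The SAP gives no formula for volume, so that step is inferred.

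**Check of the alternative.** In the same model Dose/AUCtau returns 1.000 of the true value at steady state for every assumed half-life. After exactly seven doses it returns 1.000 for half-lives up to 15 h, 1.002 at 18 h, 1.008 at 24 h and about 1.04 at 36 h. Day 7 is therefore close enough to steady state for AUCtau to serve.

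**The case against.** The strongest reply is that this is one line in an abbreviation list, probably a generic single-dose definition carried over. The bias arises only if someone extrapolates AUCinf from the Day 7 curve, and the analysis section does not describe that calculation. CL/F has no test, bound or decision attached. It is reported only where appropriate, and it is missing from the parameter lists in protocol sections 3.1 and 8.6. With no half-lives in the documents, no material error is shown for any analyte.

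Most of this stands, and it sets the severity. It does not make the formula right. The entry is the only CL/F formula in either document, CL/F and volume are planned outputs by cohort, and the readable text plans no single-dose profile to which the formula could apply.

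A reader might infer two stronger things that the documents do not support.
- **That the error distorts dose scaling or dose confirmation.** Protocol section 1.3 supports the Cohort 3 doses by scaling adult exposures on body weight and clearance capacity, not by Day 7 CL/F. The adult comparison (protocol section 8.6, SAP section 8.1) uses AUCtau, Cmax and Ctau. The 70% to 200% bounds apply to that comparison, and the dose-adjustment trigger in section 8.6 is an AUCtau percentile. SAP section 8.2 sends population PK to separate mixed-effects modelling.
- **That comparisons between age groups are distorted.** The bias factor depends on half-life. If half-life is similar across cohorts, the factor cancels in their ratio, and nothing in the documents shows that half-life differs with age.

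**Conclusion.** Wrong as written, minor severity. The SAP pairs a single-dose clearance formula with a steady-state profile and relies on an area that its analysis section does not list. If AUCinf is extrapolated from Day 7, the error is always downward. Its size runs from nothing at half-lives of 2 h or less to about one half at 24 h. That range rests on an assumed half-life, one-compartment linear kinetics and a 24-hour interval; the documents do not allow a single figure for any analyte. The consequence is limited to the descriptive CL/F and volume summaries. The primary PK endpoint, the confidence intervals against adults, dose confirmation and the population PK analysis are unaffected.

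**What to change.** In the SAP's pharmacokinetic definitions, state that for the Day 7 steady-state profile CL/F = Dose/AUCtau, and add Vz/F = Dose/(lambda_z x AUCtau), since no volume formula is given now. AUCtau is already the primary PK parameter, so no new sample, data or analysis is needed. The cost is a one-line correction plus one added definition. If the SAP is already final, its introduction provides for later changes to be documented in the clinical study report, and the formula actually used can be stated there.
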